9.4.1.2. Analyses of Secondary Endpoints

All secondary analyses will be based on the PK Set.

Dose-proportionality will be assessed across all EC mini-tablet treatments (2.5 mg, 5 mg, 10 mg, 15 mg, 30 mg ALXN1840) graphically and by using a power model ([Smith, 2000](#); [Newlands, 2006](#); [EMA, 2010](#)). The following dose-normalized PK parameters will be assessed for dose proportionality: C_{max_n} , AUC_{t_n} and AUC_{∞_n} . The log (PK parameters for plasma total and PUF Mo) will be included as a response variable and log (dose) will be included as a fixed effect in the power model:

$$\log(\text{PK Parameter}) = \mu + \beta \cdot \log(\text{Dose})$$

where $\beta = 1$ indicates perfect dose proportionality. Estimation of β , along with its 90% CI, will be provided.

Additional approaches to test dose proportionality, such as an ANOVA model, will be explored ([Calvo, 2005](#)).

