4.1.2. Dose-Proportionality Extension Period

The Dose-Proportionality Extension Period is a re-randomized, open-label, parallel group design to assess the dose-proportionality between EC mini-tablet doses.

The Dose-Proportionality Extension Period will be conducted following completion of the Two-way Crossover Periods of the study and after an at least 14-day washout period. Participants will be re-randomized as follows:

Treatment C (N=10-12): ALXN1840 2.5 mg (2 × 1.25 mg EC mini-tablets)

Treatment D (N=10-12): ALXN1840 5 mg (4 × 1.25 mg EC mini-tablets)

Treatment E (N=10-12): ALXN1840 10 mg (8 × 1.25 mg EC mini-tablets)

Treatment F (N=10-12): ALXN1840 30 mg (24 × 1.25 mg EC mini-tablets)

The 15 mg dose will not be repeated during the Dose-Proportionality Extension Period. For the purpose of evaluating dose-proportionality of the EC mini-tablet, data obtained from Treatment A of the Two-way Crossover Periods (12 × 1.25 mg EC tablets) will be included to represent a dose of 15 mg.

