6.3.2. Pharmacokinetic Set/Pharmacodynamic - Dose-Proportionality Extension Period

The Pharmacokinetic/Pharmacodynamic Set for the Dose-Proportionality Extension Period (PKDS-E) will include all participants who receive at least 1 dose of ALXN1840 in the Dose-Proportionality Extension Period and have evaluable PK data for total and/or PUF molybdenum (as surrogate measures of ALXN1840 PK) in plasma. Plasma concentrations will be summarized for all participants in the PKDS-E. The exclusions from summary statistics for total and/or PUF molybdenum plasma concentrations and/or PK parameters will be defined based on review of protocol deviations (if any) prior to database lock by PK scientist and study statistician at the discretion of the sponsor. Pharmacokinetic and pharmacodynamic analyses will be performed using the PKDS-E.

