9.5. Planned Statistical Models for PK Parameters and Concentrations

The primary analysis will be based on the PKDS-CO.

For the Period 1 and Period 2 comparisons, the PK parameters for total and PUF molybdenum (C_{max} , AUC_t , and AUC_{∞}) will be evaluated using an ANOVA statistical model with dosing period, treatment, and sequence as the fixed effects, and participant(sequence) as a random effect, using the natural logarithms of the data. Confidence intervals (CI, 90%) will be constructed for the least squares geometric mean ratio (GMR) for the 12 × 1.25 mg ALXN1840 mini-tablets versus a single 15 mg ALXN1840 tablet dose for all 3 PK parameters using the natural log-transformed data. The GMRs and the associated 90% confidence limits will be exponentiated back to the original scale.

The within-subject CV for the C_{max} , AUC_t , and AUC_{∞} will be estimated using the mean squared error from the ANOVA.

In addition, the geometric means and the associated 95% CIs of C_{max} , AUC_t , and AUC_{∞} will be reported for each treatment.

All secondary analyses will be based on the PKDS-E.

Dose-proportionality will be assessed across all EC mini-tablet treatments (2.5 mg, 5 mg, 10 mg, 15 mg, 30 mg ALXN1840) graphically and by using a power model (Smith, 2000; Newlands, 2006; EMA, 2010).

The following molybdenum dose-normalized PK parameters will be assessed for dose proportionality: C_{max_n} , AUC_{t_n} and AUC_{∞_n} . The log (PK parameters for plasma total and PUF molybdenum) will be included as a response variable and log (molybdenum dose) will be included as a fixed effect in the power model:

$$\log(\text{PK Parameter}) = \mu + \beta \cdot \log(\text{Molybdenum Dose})$$

*where $\beta = 1$ indicates perfect dose proportionality. Estimation of β , along with its 90% CI, will be provided.

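### The dose-proportionality power model has no participant effect although most data come in pairs from the same person, so the 90% CI for beta is wider than it needs to be

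*SAP*

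**What the plan says.** SAP section 9.5 writes the power model as an intercept plus a slope on log dose: "log (molybdenum dose) will be included as a fixed effect in the power model". Protocol section 9.4.1.2 has the same form: "log (dose) will be included as a fixed effect in the power model". Neither names a participant term, a random effect or a covariance structure. For the crossover comparison, SAP section 9.5 does name "participant(sequence) as a random effect".

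SAP section 4.1.2 explains where the 15 mg data come from: "The 15 mg dose will not be repeated during the Dose-Proportionality Extension Period", and Treatment A data "will be included to represent a dose of 15 mg". SAP section 4.4 has the same participants re-randomized to one of Treatments C to F.

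On the analysis set, the protocol says "All secondary analyses will be based on the PK Set" and the SAP says "All secondary analyses will be based on the PKDS-E". SAP section 6.3.2 builds PKDS-E from "all participants who receive at least 1 dose of ALXN1840 in the Dose-Proportionality Extension Period" with evaluable PK data; it does not say that their earlier Treatment A records belong to the set. SAP section 9.6 lists no deviation from the protocol.

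**The concern.** The proportionality data are mostly pairs: one value at 15 mg and one at another dose in the same person. A model with only an intercept and log dose leaves the between-participant variance in the error term and ignores the pairing. Beta with its 90% CI is the only model-based result that the SAP specifies for the secondary objective, and it rests on 10 to 12 participants per Extension dose. An interval wider than the data support blurs that answer.

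There is a second issue. All 15 mg values are collected before all other doses. A systematic difference between the crossover and the Extension is therefore partly confounded with dose, and no planned analysis estimates it.

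**Working it through.** **The plan's own figure.** The plan gives no SE, CI width or power for beta. The only related figure is enrolment: 40 / (1 − 0.15) = 47.1, rounded up to 48, which matches SAP section 4.3.

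**Inputs.** Doses 2.5, 5, 10, 15 and 30 mg (SAP 9.5); 10 to 12 per Extension arm (SAP 4.1.2); 90% CI (SAP 9.5). I take the molybdenum dose as proportional to the ALXN1840 dose, so only the intercept changes. CVs are **assumed**, with log-scale variance ln(1 + CV²).

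**Layout, 10 per arm (80 values, 40 people).**
- Mean log dose is 2.383. Log 15 lies 0.325 above it; the other four doses average 0.325 below it.
- Sxx = 42.16.
- The cross-product within pairs is negative. With within-person correlation ρ, the true variance of the ordinary least-squares (OLS) slope is σ²/Sxx × (1 − 0.20ρ). OLS reports about σ²/Sxx, so its interval is conservative for any positive ρ.

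**Worked case, between 30% and within 20%.** Between-participant variance is ln 1.09 = 0.0862 and within-participant variance is ln 1.04 = 0.0392. The total is 0.1254 and ρ = 0.687.
- As written: expected reported SE 0.0543, half-width 1.665 × 0.0543 = 0.090 (78 df). True SE = √(0.1254/42.16 × (1 − 0.201 × 0.687)) = 0.0506. The ratio is 1.07, which implies coverage of about 93%.
- Random intercept: within-pair differences in log dose have sum of squares 50.62, and the pair sums have centred sum of squares 33.69. Information = 50.62/(2 × 0.0392) + 33.69/(2 × (0.0392 + 2 × 0.0862)) = 645.7 + 79.6 = 725.3. SE = 0.0371, half-width 1.685 × 0.0371 = 0.063 (39 df).
- Random intercept plus a crossover-versus-Extension term: the differences are centred too, so information = 33.69/0.0784 + 79.6 = 509.3. SE = 0.0443, half-width 0.075.

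**Half-width of the 90% CI for beta, 10 per arm.**

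| Between/within CV (assumed) | As written | Random intercept | Ratio | Intercept + crossover-vs-Extension term |
|---|---|---|---|---|
| 10/40% | 0.102 | 0.102 | 1.00 | 0.115 |
| 20/40% | 0.111 | 0.108 | 1.03 | 0.123 |
| 30/30% | 0.106 | 0.089 | 1.19 | 0.104 |
| 30/20% | 0.090 | 0.063 | 1.45 | 0.075 |
| 40/20% | 0.111 | 0.064 | 1.73 | 0.077 |
| 50/15% | 0.126 | 0.049 | 2.57 | 0.060 |

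With 12 per arm the ratios agree to within 0.01. In simulation without a shift (3,000 trials per scenario), coverage as written was 90.5% (10/40%), 91.9% (30/30%), 92.9% (30/20%) and 93.4% (50/15%); the mixed model gave about 90% throughout.

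**What the widths mean.** The extreme doses differ 12-fold, so a half-width h is a factor of 12^h on the dose-normalized exposure ratio between them. At 30/20% that is 12^0.090 = 1.25 as written against 12^0.063 = 1.17.

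**Sensitivity to a crossover-versus-Extension shift.** Bias in beta per unit log shift:
- As written: 40 × (−0.325)/42.16 = −0.31.
- Random intercept at 30/20%: the differences in log dose sum to −26.03, so (−26.03/0.0784)/725.3 = −0.46.

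With an assumed shift of 0.10 (about 10% in exposure) at 30/20%, simulated coverage is 87% as written, 69% with the participant intercept and 89% once the crossover-versus-Extension term is added.

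**Analysis set.** Eight more participants with only a 15 mg value would cut the SE of beta by 0.1–0.9%.

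**The case against.** The strongest reply is that nothing is invalid. Beta is unbiased when there is no shift, coverage is at or above nominal, and the plan sets no acceptance range for beta and no precision target, so no decision is shown to change. The size rests on assumed CVs and is nil at 10/40%. All of this stands, and it limits the point to precision.

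The reply also has force against the remedy. The random intercept is less robust to a crossover-versus-Extension shift. With a shift of 0.10, a normal approximation gives coverage at 50/15% of about 49%, against 91% as written. The root mean squared error of beta is then equal for the two models at 30/30% (0.068) and 30/20% (0.059), although the mixed model still does better at 40/20% and 50/15%. This is why the sensitivity analysis must accompany the change.

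It can also be said that checks exist: a period effect in the crossover ANOVA, a washout of at least 14 days justified in protocol section 4.2, graphical assessment, and exploratory ANOVA approaches in protocol section 9.4.1.2. The crossover period effect separates Period 1 from Period 2 only. None of the four estimates a shift between the crossover and the Extension.

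Finally, the intent to include Treatment A data is readable from SAP section 4.1.2 and the five-dose list in SAP section 9.5. That is fair; the set-name mismatch is a wording matter with negligible numerical effect.

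**Conclusion.** The concern holds. The written model ignores the pairing that the design creates, and its interval for beta is inefficient and mildly conservative for any positive within-participant correlation. The loss in width runs from none (10/40%) to a factor of 2.57 (50/15%), with 1.19 to 1.45 at 30/30% and 30/20%. The calculation assumes one common within-person correlation, random Extension assignment, complete pairs and, for the width comparison, no crossover-versus-Extension shift. With that term in the model, the net gain over the written model is about nil at 30/30% (0.104 against 0.106) and negative at 10/40% (0.115 against 0.102). The term therefore belongs in a sensitivity analysis. This should be changed, but it does not invalidate the plan.

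**What to change.** In SAP section 9.5, specify the power model as a linear mixed model: log(PK parameter) = μ + β·log(dose) + random participant intercept. Name the degrees-of-freedom method and report β with its 90% CI.

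As a sensitivity analysis, add a crossover-versus-Extension term and report whether β moves.

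State that Treatment A mini-tablet records (PKDS-CO) and Treatment C to F records (PKDS-E) both enter. Reconcile PKDS-E in SAP section 9.5 with the PK Set in protocol section 9.4.1.2, and list any change in SAP section 9.6. The BMI stratum may be added to match the randomization; no gain in precision is claimed for it.

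The cost is SAP wording, one changed procedure call and one further run, with no new data. The sensitivity interval is wider than the main one (for example 0.075 against 0.063 at 30/20%). If a participant effect was always intended, one sentence settles the main point.

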4.4. Treatment Assignment and Blinding

- This is an open-label, 2-period, 2-sequence study where, in order to minimize selection bias in

This document is confidential.

treatment assignment, each participant will be randomized to one of 2 treatment sequences (Treatment A and B) in the Two-way Crossover Periods. The randomization will be stratified by Baseline BMI. Two strata for Baseline BMI (< 25, 25 to < 32 kg/m²) will be used.

- Eligible participants who meet all inclusion and no exclusion criteria included in the study will be assigned unique study participant numbers during randomization to one of 2 treatment sequences (Treatments A and B). Study participant numbers will not be reallocated once assigned.
- Participants will be re-randomized in the Dose-Proportionality Extension Period to one of 4 treatment sequences (Treatments C, D, E, and F). The re-randomized treatment assignment will be based on Baseline BMI as for the Two-way Crossover Periods, with 2 strata for Baseline BMI (< 25, 25 to < 32) to be used. Block randomization will be used to equally randomly assign participants to each treatment.

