8.3. Demographic and Baseline Characteristics

Demographic and baseline characteristics, including age, sex, race, ethnicity, child-bearing potential, height, body weight, and BMI will be summarized using standard descriptive statistics. No formal statistical comparisons between populations will be performed. Demographics and informed consent data will be listed for all participants in the Enrolled Set.

Height (in cm) = height (in inches) * 2.54

Weight (in kg) = weight (in lbs) * 0.4536

This document is confidential.

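### The dose-proportionality model omits the BMI stratum, body weight and any participant term, so the slope's 90% CI is probably wider than the collected data require (a minor efficiency point).

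*SAP*

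**What the plan says.** SAP 9.5 regresses the log PK parameter on an intercept and log dose only: "log (molybdenum dose) will be included as a fixed effect in the power model". Protocol 9.4.1.2 has the same single-regressor form (log dose "will be included as a fixed effect in the power model"). The slope is to be reported "along with its 90% CI, will be provided", with no acceptance range or precision target.

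On allocation, SAP 4.4 says "The re-randomized treatment assignment will be based on Baseline BMI as for the Two-way Crossover Periods". The two strata are split at a BMI of 25 kg/m². On the allocation ratio the same section adds: "Block randomization will be used to equally randomly assign participants to each treatment". Arms are small; for example "Treatment C (N=10-12): ALXN1840 2.5 mg (2 × 1.25 mg EC mini-tablets" in SAP 4.1.2, with the same range for D, E and F. The 15 mg point is not a separate arm. SAP 4.1.2 takes it from Treatment A of the crossover, that is, from the same people.

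Body size is available. Protocol 8.2.1 records height and weight at Screening, and under SAP 8.3 "height, body weight, and BMI will be summarized using standard descriptive statistics". Its only other analytic use is in the exploratory clearance plots and correlation of SAP 10.1.2.

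**The concern.** Three sources of explainable variation are left in the residual of the only model for the secondary objective: the stratum that governed re-randomisation, body weight, and participant. The participant term matters most, because two records from one person share everything stable about that person, body size included. The crossover ANOVA in the same SAP section has a participant effect; the power model does not. It therefore treats paired records as independent and forgoes the within-participant comparison of 15 mg with the other dose.

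What is at stake is the width of the reported 90% CI for beta. The tested doses are meant to cover the planned paediatric range (protocol 4.3), and the sample size rests on practicality and convention (SAP 4.3), so nothing in the plan guarantees that the unadjusted interval will be tight enough to be informative.

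**Working it through.** **The plan's own figure.** The only sample-size figure that can be reproduced is enrolment: 40 / (1 - 0.15) = 47.06, rounded up to 48 (check: 48 x 0.85 = 40.8). The plan states no precision for beta.

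**Design inputs (SAP 4.1.2 and 4.4).** 12 participants at each of 2.5, 5, 10 and 30 mg, plus 48 records at 15 mg from the same participants. Molybdenum dose is a constant multiple of ALXN1840 dose, so the spread of log dose is unaffected by which is used.

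The ln(dose) values are 0.916, 1.609, 2.303, 3.401 and (15 mg) 2.708. Mean = [12 x (0.916 + 1.609 + 2.303 + 3.401) + 48 x 2.708] / 96 = 2.383. The sum of squares about it is Sxx = 50.59. For the model as written, SE(beta) = sigma / sqrt(50.59) = 0.141 sigma, and the 90% half-width is t(0.95, 94) x SE = 1.661 x 0.141 sigma. With 10 per arm plus 40 at 15 mg, Sxx = 42.15 and SE = 0.154 sigma.

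**Assumptions (none is in the documents).** Between-participant SD apart from weight 0.20-0.35; within-participant SD 0.15-0.20; SD of ln(weight) about 0.15; exposure varying with weight to the power 0.75-1. Then sigma² = between² + (exponent x 0.15)² + within².

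**Body-size terms only.** Simulation of 48 participants (BMI 18 to <32, 50-100 kg, blocks of four within BMI stratum), fitted by ordinary least squares. Entries are 90% half-widths for beta; the change from no covariate is in brackets.

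| Between SD | Exponent | No covariate | + BMI stratum | + BMI stratum + ln(weight) |
|---|---|---|---|---|
| 0.20 | 0.75 | 0.063 | 0.061 (-3%) | 0.058 (-8%) |
| 0.20 | 1 | 0.067 | 0.064 (-4%) | 0.058 (-13%) |
| 0.25 | 0.75 | 0.079 | 0.077 (-3%) | 0.074 (-6%) |
| 0.35 | 0.75 | 0.097 | 0.095 (-2%) | 0.093 (-4%) |

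A check that needs no weight model: if body size explains a share R² of the residual variance, the CI shrinks by 1 - sqrt(1 - R²). That is 0% at R² = 0, 2.5% at 0.05, 5% at 0.10, 10.5% at 0.20 and 16% at 0.30. The degrees-of-freedom cost is about 0.1% or less.

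**Participant random effect.** The covariance has rho = (between² + weight variance) / sigma² within a person, and the generalised least squares SE is compared with the SE that the planned model would report. For the first row with within SD 0.15: sigma² = 0.0400 + 0.0127 + 0.0225 = 0.0752, sigma = 0.274, rho = 0.0527 / 0.0752 = 0.70. The planned half-width is 1.661 x 0.141 x 0.274 = 0.064; with the participant term it is 0.043.

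| Between SD | Within SD | Exponent | rho | Planned | + participant | Narrower | Further gain from body size |
|---|---|---|---|---|---|---|---|
| 0.20 | 0.15 | 0.75 | 0.70 | 0.064 | 0.043 | 33% | 1.1% |
| 0.20 | 0.15 | 1 | 0.74 | 0.068 | 0.043 | 37% | 1.8% |
| 0.25 | 0.20 | 0.75 | 0.65 | 0.079 | 0.057 | 29% | 0.8% |
| 0.35 | 0.20 | 0.75 | 0.77 | 0.098 | 0.058 | 41% | 0.3% |

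The algebra gives 29-41%; simulation of the same settings gives about 28-40%. Crossing the assumed SDs freely widens the range to 22-54%, with 0.2-2.3% further from body size. If participants differ less (rho = 0.3), the participant term gains only 7%.

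Part of this gain is a correction of the reported interval. At rho = 0.7 the unadjusted slope has a true SE of 0.130 sigma, while the model would report 0.141 sigma. The planned CI is therefore conservative as well as inefficient.

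**The case against.** The strongest reply is that an unadjusted power model is a recognised analysis, that body size is explored separately in SAP 10.1.2, and that no decision turns on the difference. The plan reports beta and a CI without limits, and the body-size terms move the half-width by at most 0.009. All of that stands. It limits the severity but does not remove the point. Protocol 9.4.1.2 does leave room for additional approaches such as an ANOVA model, but the SAP does not carry this over and names no covariates.

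A reader might infer more than the documents support:

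- *That beta is biased or its CI invalid.* Leaving a stratification factor out of the model does not bias the slope, and the CI is if anything too wide. Chance weight imbalance between arms of 10-12 is ordinary sampling error already inside that CI, not an extra harm.
- *That this is a purely parallel-group comparison, so body-size terms are the main remedy.* Treatment A supplies a paired 15 mg record. A participant term absorbs weight, BMI and every other stable difference, and leaves little for body size to add.
- *That the sponsor expects body size to drive clearance.* The exploratory objective is to look for a relationship; it does not assert one. The weight-based allometry in protocol 4.3 makes an effect plausible, but gives no coefficient for adults of 50-100 kg.
- *That one magnitude applies to every endpoint.* The assumed effect acts through clearance and so bears most directly on total Mo AUC. Its size for C_max and for PUF Mo is less certain.

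**Conclusion.** The point holds as a matter of efficiency, not validity, and is minor. The omission of all three terms is plain in SAP 9.5 and protocol 9.4.1.2. Under the assumed variances, the participant term is worth about 28-40% of the CI width. The body-size terms are worth about 4-13% if used alone (2-5% for BMI stratum by itself), but only about 1% once the participant term is present. They are worth nothing if body size is unrelated to exposure. Confidence in the omission and in the direction of the effect is high. The percentages rest on assumed variances and an assumed weight exponent.

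**What to change.** In SAP 9.5, specify log(PK parameter) = mu + beta x log(molybdenum dose) + BMI stratum, optionally + ln(Screening body weight), with participant as a random effect and the Treatment A and C to F records both included. Keep the model with log(dose) alone as a sensitivity analysis. Record the change in SAP 9.6 and 14, since the protocol gives the single-regressor form.

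The cost is a line or two of SAP text, one variance component and at most two fixed-effect degrees of freedom, with no new data. Settling it before database lock also avoids choosing covariates after the weight-clearance plots have been seen.

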9.6. Deviation from Analyses Planned in Protocol

Not applicable.

10. Exploratory Analysis

10.1.1. Endpoints

The endpoints are: Clearance of total molybdenum, clearance of PUF molybdenum, covariates such as body weight (kg), and BMI(kg/m²).

10.1.2. Analysis of the Endpoint

Exploratory analyses as described in this section will be performed using the PKDS-CO and PKDS-E.

Box-whisker plots for two strata of BMI (< 25, 25 to < 32 kg/m²) (on X-axis) and corresponding molybdenum dose normalized clearance of total molybdenum and PUF molybdenum (on Y-axis) will be presented.

For body weight, a scatter plot with a Pearson correlation will be presented with body weight on X-axis and clearance of total molybdenum and PUF molybdenum on Y-axis to demonstrate if any correlation exists between the two. If needed, Pearson correlation analyses may be performed.

This document is confidential.

11. Pharmacodynamics

Samples for assessment of plasma total copper and PUF copper will be used for the PD analysis described in this SAP/section. Samples for the assessment of ceruloplasmin (Cp), ceruloplasmin-bound copper (CpC), non-ceruloplasmin-bound copper (NCC), and LBC will be retained and may be analyzed in the future.

Plasma samples of total copper and PUF copper will be collected on Day 1: Pre-dose, 1, 2, 3, 4, 5, 6, 8, 12 hours post-dose, Day 2, 3, 4, 5, 6, 7, 8, 9, 10, 11 of each treatment period, details have been provided in [Section 4.6](#).

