For patients aged 3 to < 6 years, the population PK modeling results showed that a 5 mg dose has comparable exposure to 15 mg administered to adult patients, and that a 15 mg dose has a higher exposure than 30 mg, but a lower exposure than 60 mg administered to adult patients. Hence, the predicted dose range for patients aged 3 to < 6 years is 5 mg to 15 mg, which is anticipated to provide comparable safety and efficacy outcomes to those in adolescent and adult patients over 12 years of age with a dose range of 15 mg to 60 mg currently allowed in the ongoing Phase 3

Study WTX101-301. Therefore, the EC mini-tablet doses of 2.5, 5, 10, 15, and 30 mg will be tested in this study, which covers the entire anticipated dose range recommended in the planned study in the pediatric population.

An inductively coupled plasma-mass spectroscopy (ICP-MS) method, with a lower limit of quantification (LLOQ) of 1.00 ng/mL and 0.25 ng/mL for the assays of total Mo and PUF Mo, respectively, has been previously implemented for analyzing plasma samples from Study WTX101-HV-106. In that study, for the 15 mg and 60 mg doses, %AUC_{extrap} ranged from 1.3% - 12.2% (all were less than 20%). In the current study, a maximum observed concentration (C_{max}) for total Mo of approximately 40 ng/mL is anticipated after the lowest ALXN1840 dose of 2.5 mg and with an assay LLOQ of 1.00 ng/mL, it would be possible to detect measurable total Mo concentrations at a mean of 1.25 ng/mL for approximately 5 half-lives with reasonably low expectation for excess AUC extrapolation of over 20% for AUC_∞ estimation. A C_{max} for PUF Mo of approximately 2 ng/mL is anticipated after the lowest ALXN1840 dose of 2.5 mg and with an assay LLOQ of 0.25 ng/mL, it would be possible to detect measurable PUF Mo concentrations at a mean of 0.25 ng/mL for approximately 3 half-lives with possibility of AUC extrapolation of over 20% for AUC_∞ estimation.

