5.4. Exploratory Endpoints

- CL/F, body weight, and BMI
- Absolute and percent changes from pre-dose baseline of plasma copper concentrations: total copper and PUF copper

This document is confidential.

6. Analysis Sets

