9.2. Plasma PK Endpoint

Following PK parameters will be derived from the plasma concentrations of total and PUF molybdenum when feasible and supported by the available data.

- Time delay between the time of dosing and time of appearance of drug concentration in plasma (Tlag; for plasma total molybdenum with ALXN1840 administration)
- Maximum observed concentration in plasma (C_{max})
- Molybdenum dose-normalized C_{max} (C_{max_n}); n = dose normalized
- Time to C_{max} (T_{max})
- Area under the plasma concentration (AUC) versus time curve from time 0 to the last quantifiable concentration (AUC_t)
- Molybdenum dose-normalized AUC_t (AUC_{t_n})
- AUC versus time curve from time 0 to infinity (AUC_{∞})

This document is confidential.

- Molybdenum dose-normalized AUC_{∞} (AUC_{∞_n})
- AUC extrapolated from time t to infinity as a percentage of total AUC_{∞} ($\%AUC_{\text{extrap}}$)
- Apparent terminal-phase elimination rate constant (λ_z)
- Terminal elimination half-life ($t_{1/2}$)
- Apparent oral clearance (CL/F)
- Apparent volume of distribution (V_d/F)
- Relative bioavailability (F_{rel}) between test and reference treatments

Additional plasma PK parameters may be calculated if deemed appropriate.

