9.4. Derivation of Pharmacokinetic Parameters

- The apparent C_{max} and the corresponding t_{max} along with T_{lag} will be read directly from the concentration-time plot (observed data).
- AUC_t will be calculated using the log-linear trapezoidal interpolation rule for extravascular model.
- The terminal elimination rate constant (λ_z) will be determined by log linear regression obtained on at least the 3 last quantifiable concentrations and will not include C_{max} ; $t_{1/2}$ is calculated by the program as $\ln 2/\lambda_z$;
- AUC_{∞} will be calculated by the program as: $AUC_{\infty} = AUC_t + AUC_{extrap}$ where last is the sampling time point of the last measurable concentration (t_{last}). AUC_{extrap} will be calculated by the program as: C_{last}/λ_z , where C_{last} is the observed concentration at time t_{last} and λ_z is the elimination rate constant during the apparent terminal elimination phase. AUC_{∞} will only be presented for participants with a reliable λ_z ;
- CL will be calculated by program as (molybdenum dose amount/ AUC_{∞});
- V_z will be calculated by the program as (molybdenum dose amount/ AUC_{∞})/ λ_z ;
- Dose normalized PK parameters will be calculated using the equivalent molybdenum dose and not the ALXN1840 dose. .

The following PK acceptance criteria will be applied to assess the reliability of elimination parameters:

- Number of points to calculate λ_z is greater than or equal to 3 excluding C_{max} point;
- The adjusted square of the correlation coefficient or coefficient of determination (Rsquare adjusted) for the goodness of fit of the regression line through the data points must be ≥ 0.90 ;
- $AUC_{extrap} \leq 20\%$.

Unreliable PK parameters will be listed but flagged and excluded from summary.

This document is confidential.

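### SAP 10.1.2 labels the BMI box-plot axis as dose-normalized clearance although CL/F is already dose over AUC∞, and commits to BMI only as two groups split at 25

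*SAP*

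**What the plan says.** The exploratory objective (Protocol 3, Table 4; SAP 3) is to explore how total Mo and PUF Mo clearance relate to body weight in kg and BMI in kg/m². SAP 5.4 gives the endpoint as "CL/F, body weight, and BMI", and SAP 10.1.1 gives it as "Clearance of total molybdenum, clearance of PUF molybdenum, covariates such as body weight" and BMI. Neither mentions a dose-normalized clearance. Protocol 9.4.1.3 leaves the method to the SAP.

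SAP 10.1.2 applies to both PKDS-CO and PKDS-E and commits to two displays:

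- **BMI:** box-whisker plots for the two randomization strata, with "corresponding molybdenum dose normalized clearance of total molybdenum and PUF molybdenum (on Y-axis) will be presented".
- **Weight:** a scatter plot with a Pearson correlation, with plain clearance on the vertical axis.

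A closing sentence in the weight paragraph allows further Pearson correlations if needed. It does not name BMI.

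On derivation, SAP 9.4 states "CL will be calculated by program as (molybdenum dose amount", with AUC∞ as the divisor. It adds: "Dose normalized PK parameters will be calculated using the equivalent molybdenum dose and not the ALXN1840 dose". SAP 9.2 lists molybdenum dose-normalized forms of Cmax, AUCt and AUC∞, and lists CL/F once, without such a form.

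**The concern.** There are two separate points.

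First, the variable named on the BMI axis is not one the SAP derives. Dose is already in the numerator of CL, so a programmer who applied the dose-normalization rule to the label would divide by dose again and plot 1/AUC∞. The two plots serving one objective would then show different quantities.

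Second, the objective names BMI as a measurement in kg/m², but the only BMI analysis the SAP commits to reduces it to two groups. Weight, the other body-size measure, is analysed continuously. At stake is how clearly the study can describe the relation between CL/F and BMI.

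**Working it through.** The documents give no precision or power figure for this analysis, so there is nothing of the plan's own to reproduce.

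**Label.** Inputs: CL = molybdenum dose/AUC∞ (SAP 9.4); extension doses 2.5, 5, 10 and 30 mg (SAP 4.1.2).

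- Suppose AUC∞ = k × Dose^b. Then CL is proportional to Dose^(1−b), and CL divided again by dose is proportional to Dose^(−b). The fixed molybdenum fraction cancels in ratios between doses.
- Under dose proportionality (b = 1), CL is the same at every dose. CL/dose relative to 30 mg is 30/2.5 = 12 at 2.5 mg, 30/5 = 6 at 5 mg and 30/10 = 3 at 10 mg.
- For assumed b of 0.8 and 1.2, the ratio of 2.5 mg to 30 mg is 12^0.8 = 7.3 and 12^1.2 = 19.7 for CL/dose. For CL itself it is only 0.61 and 1.64.
- In PKDS-CO every dose is 15 mg, so a second division is a constant rescaling that leaves the picture unchanged. The same holds in any single-dose panel.
- Extension re-randomization is stratified by the same two BMI strata (SAP 4.4), so dose should be roughly balanced between boxes. A second division would widen both boxes rather than shift one against the other.

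**Split at 25.** Input: enrolled BMI range 18 to below 32 kg/m² (Protocol 5.1). The BMI distribution is not given and is assumed. The share of information kept about a linear relation is the squared correlation between BMI and the stratum indicator.

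- Uniform on 18–32: the half-means are 21.5 and 28.5, so the share is 0.25 × 7² / (14²/12) = 12.25/16.33 = 0.75.
- Normal with an even split: φ(0)²/0.25 = 0.159/0.25 = 0.64.
- Normal truncated to 18–32, mean 23 to 27: 0.60–0.66 with SD 3, 0.54–0.65 with SD 2.5, and 0.64–0.68 with SD 3.5.

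The range over these assumptions is roughly 54–75%.

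**The case against.** The strongest reply on the label is that the literal reading needs a parameter the SAP never derives. SAP 9.4 uses dose normalization to mean the molybdenum-equivalent dose in place of the ALXN1840 dose, and every endpoint statement names plain clearance or CL/F. This stands: the benign meaning is the likelier one. What remains is that no passage corrects the label and that the two plots in one section differ.

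A reader might go further and infer that the PKDS-E plot would mainly display dose. The documents do not support that. It needs the less likely reading of the label and also pooling of the extension arms, and SAP 10.1.2 does not instruct pooling. SAP 7.1 leans towards presentation by treatment, although its extension tables also carry a total column and it refers layout to table shells. For PUF Mo the spread could be smaller. Protocol 4.3 anticipates at 2.5 mg "approximately 3 half-lives with possibility of AUC extrapolation of over 20" percent, and SAP 9.4 says "Unreliable PK parameters will be listed but flagged and excluded from summary". If all 2.5 mg values dropped out, the spread would be 30/5 = 6-fold. But the protocol speaks only of a possibility, and the SAP rule names summaries, not plots.

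On BMI, the cut at 25 is the prespecified randomization stratum, the objective is only to explore, and the optional Pearson sentence could reach BMI. That is fair, and it makes the box plot a reasonable display to keep. It does not explain why one body-size measure gets a committed continuous analysis and the other does not.

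It is also tempting to require every plot and correlation to be split by treatment. That would be a real change with a cost: extension correlations would rest on 10–12 participants each. For an assumed true correlation of 0.4 (Fisher z, two-sided 0.05), power is Φ(0.424 × √(n−3) − 1.96): about 20–25% at n = 10–12, against about 73% at n = 40.

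**Conclusion.** The point holds as a minor clarification and a nearly free improvement. The BMI axis label is inconsistent with the SAP's own definition of CL and with its endpoints, and most likely means CL from the molybdenum-equivalent dose. A distorted display, up to 12-fold under dose proportionality, arises only if the label is taken literally and the extension arms share a box. Even then it is added noise rather than bias, and PKDS-CO is untouched. Independently of the label, the committed BMI analysis keeps roughly 54–75% of the information on a linear relation. That figure rests on assumed BMI distributions and measures efficiency only, since the plan sets no test or precision target here. Nothing in the primary, secondary or safety analyses depends on this.

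**What to change.** In SAP 10.1.2:

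- **(a)** Rename the BMI box-plot variable as CL/F as derived in Section 9.4. This is correct under either reading of the label.
- **(b)** Keep the box plot and add a scatter plot with Pearson correlation of CL/F against continuous BMI, handled as for weight.
- **(c)** For these displays, show Treatments A and B separately in PKDS-CO, so that no participant counts twice in one correlation. In PKDS-E each participant has one CL/F value per analyte, so the arms may be shown together with dose marked.

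The cost is a few sentences of SAP text and minor programming. BMI is already summarized as a continuous variable (SAP 8.3) and CL/F is already derived (SAP 9.2), so no new data are needed.
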